5.2.6 Marginal Bone Level Changes

Bone level changes will be evaluated on a standardized peri-apical radiograph at implant loading and at 12, 24, 36, 48, and 60 months post-loading. The radiographs will be sent to a centralized location to be evaluated in a blinded fashion by a single reader using a calibrated measuring tool. Additional details will be provided in operations manual to describe how the central radiologist will measure the bone level values from the radiographs.

5.2.7 Buccal Bone Dimensional Changes

Cone beam computed tomography will be utilized to measure the dimensional thickness of buccal plate of the localized area around the implant at screening, implant loading and at 12, 24, 36, 48 and 60 months post-loading. Additional details will be provided in operations manual to describe how the central radiologist will measure the bone level values from the CBCT scans.

5.2.8 Implant Success and Survival

Implant survival will be assessed at all visits following the surgical visit. A surviving implant is an implant that is in place at the time of follow-up.

Implant success will be assessed at implant loading, and at 12, 24, 36, 48, and 60 months post loading. A successful implant will meet all of the following criteria according to Buser¹⁶:

- Absence of persistent subjective complaints, such as pain, foreign body sensation, and/ or dysesthesia
- Absence of a recurrent peri-implant infection with suppuration
- Absence of mobility
- Absence of a continuous radiolucency around the implant

[figure not shown]
Non-surviving implants will be counted as an unsuccessful implant.

Any dental implant showing excessive bone loss, radiolucency, or infection shall be treated in the manner best suited to the well-being of the subject, including treatment to save the dental implant. Continuous radiolucency, implant mobility, and recurrent perimplant infection with suppuration shall be recorded on the adverse event form (see section 7.3.4).

5.2.9 Soft Tissue Evaluation

Gingival recession and papilla height will be evaluated according to Grunder¹⁷, recording changes in gingiva/mucosa and papilla margins over time. The soft tissue will be evaluated at final restoration, and at 12, 24, 36, 48, 60 months post-implant loading. The following measurements will be recorded in millimeters:

- Measurement CLT_m and CLT_d length of the crown from highest point of soft tissue margin to the incisal edge of the adjacent mesial and distal teeth
- Measurement CLI length of the implant crown from highest point of the soft tissue margin to the incisal edge
- Measurement IP_m and IP_d distance from the top of the papilla to the incisal edge mesial and distal of the implant crown

5.2.10 Subject Satisfaction

Subject satisfaction will be assessed utilizing Visual Analogs Scales (VAS) at 12, 24, 36, 48, and 60 months post implant loading for the following parameters related to the implant and restoration:

- Level of pain associated with the implant and crown Painful → No pain
- Level of satisfaction with the function of the implant supported crown Not satisfied at all → Highly satisfied
- Level of satisfaction with the esthetics of the implant supported crown Not satisfied at all → Highly satisfied

Each subject will be asked to complete a VAS for each of the above parameters by the Investigator. The subject will be given a paper questionnaire to mark their responses on the VAS (Appendix 3). The subject will mark a 100 mm scale with a vertical line. A measurement will be made from the left on the scale to the point of the first marking from the subject. This measurement will be recorded on a case report form.

5.2.11 Intra-Oral Photographs

Intra-oral photographs will be taken at each study visit to show the pre-operative situation, the implant in place in the bone at surgery, the temporary restoration, the final restoration and the final crown at all follow-up visits. Additional photographs are optional and can be taken to fully document the case.

Each photograph should be labeled with the subject's study identification number and visit date.

5.3 Protocol Related Procedures

5.3.1 Screen Failures

Any subject that signs the Informed Consent Form must be entered into the electronic database. Subjects will be evaluated based on the inclusion and exclusion criteria for initial eligibility during the screening visit and re-evaluated after tooth extraction. Any subjects that are determined to be ineligible prior to be randomized, will be considered screen failures. Screen failures will be documented by completing a Screen Failure Case Report Form.

5.3.2 Early Withdrawal

Any subject may withdraw from the study at any time without prejudice and will be offered an alternative treatment for his/her dental condition. Subjects will be advised of the need for the prescribed follow-up visits for their ongoing care, well-being, and collection of any safety data.

The Investigator may withdraw any subject from the study in the case of:

- Non-compliance with the protocol
- Failure to attend the follow-up visits
- Serious Adverse Event (SAE) or adverse event, which in the opinion of the Investigator prevents the subject's further participation in the study.
- Failure to achieve primary stability if primary stability is not obtained and the implant is removed, the patient will be withdrawn at the time of implant removal.
 No further follow up is necessary.
- No study implant placed if the study implant is never placed, regardless of reason, the patient will be withdrawn. No further follow up is necessary.

The subject withdrawal will be documented on a Study Termination/ End of Study CRF and must include the reason for the subject withdrawal. Efforts should be made to capture the primary study endpoint for each subject prior to withdrawal, if possible. If the subject fails to attend follow-up visits, at least three attempts to reach the subject must be documented; with at least one of the attempts made by certified letter.

Withdrawn subjects will not be replaced.

5.3.3 End of Study

Once the subject is seen for the final visit at 60-months post-loading, the subject will have completed the study. This will be documented on a Study Termination/ End of Study CRF.

5.3.4 Subject Replacement Policy

Subjects who have been randomized will not be replaced.

5.3.5 Protocol Deviations

Deviations from the procedures established in the protocol are not permitted. If a deviation occurs, the study center must record the deviation on the appropriate CRF. The sponsor shall be notified immediately of any deviations in informed consent, inclusion/exclusion criteria, and randomization procedures. The IRB should be notified according to the requirements of the local IRB.

Any deviation from the protocol (including deviations from the expected study visit windows) may jeopardize the study outcome. Non-compliance of the subjects, as well as of the Investigators, may lead to the closure of the respective study center.

6 Schedule of Assessments

An overview of the schedule of assessments is provided in a table format after the protocol synopsis.

6.1 Visit Windows

Subjects need to be seen within the following windows:

Visit #	Visit Name	Visit Window
Visit 1	Screening	< 45 days from tooth extraction
Visit 2a	Tooth Extraction and Randomization Bone grafting of the extraction socket	
Visit 2b	Implant Surgery	Immediately at tooth extraction or 17 weeks ± 1 weeks after tooth extraction

Visit 3	Immediate Post-Operative	10 days ± 3 days after implant surgery
Visit 4*	Uncover Implant	10 weeks ± 3 weeks after implant surgery
Visit 5*	Implant Loading/ Temporary Restoration	10 weeks ± 3 weeks after implant surgery
Visit 6	Impression	5 weeks ± 1 week post-loading
Visit 7	Final Restoration	10 weeks ± 2 week post-loading
Visit 8	6-month follow-up	6 months ± 1 month post-loading
Visit 9	Primary Endpoint	12 months ± 1 month post-loading
Visit 10	Additional follow-up	24 months ± 1 month post-loading
Visit 11	Additional follow-up	36 months ± 1 month post-loading
Visit 12	Additional follow-up	48 months ± 1 month post-loading
Visit 13	Additional follow-up	60 months ± 1 month post-loading

*Note: Uncovering the implant and implant loading may be done at the same visit at the discretion of the investigator.

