3.3 Study Treatments

Subjects needing a single tooth extraction and replacement with a dental implant in the anterior or pre-molar region of the maxilla or mandible will be screened to determine study eligibility. Following tooth extraction, the inclusion and exclusion criteria will be reevaluated, and if the subject continues to be eligible, the surgeon will proceed with randomization, bone grafting of the extraction socket with Straumann allograft and implant placement. Subjects randomized into the test group will receive bone grafting of the extraction socket and an implant during the same surgical procedure as the tooth

extraction. Subjects randomized into the control group will also undergo bone grafting of the extraction socket with Straumann allograft and eturn for a second surgery after 4 months of healing.

After randomization the subject is considered enrolled in the study.

Ten days following implant placement, subjects will be evaluated for healing and possible suture removal in cases when non-resorbable sutures are used. The subject will return in 8 weeks following implant placement to uncover the implant. An index or impression will be taken for provisional fabrication. Contingent upon good primary stability, the implant will be loaded in appropriate occlusion with an abutment and temporary prosthesis at 10-12 weeks post implant placement. Note that implant loading may be done at the same visit as uncovering the implant at the discretion of the investigator.

The definitive impression will be taken at 4-6 weeks following implant loading and the final prosthesis will be seated at 8-12 weeks following implant loading.

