5.1.11 Adverse Event Check

At each visit the Investigator should determine if any adverse events occurred since the last study visit by speaking with the subject and reviewing any dental and medical records. These Adverse Events (AEs), along with any adverse events from the current study visit, should be documented and reported as descried in Section 7 of the protocol. In addition the Investigator should evaluate the status of any ongoing adverse events throughout the study as specified in Section 7.4.

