6.4 Visit 2b – Implant Surgery

The timing of Visit 2b will depend on the treatment group assigned during randomization. For subjects randomized to the test group, the implant will be placed immediately after tooth extraction and bone grafting of the extraction socket. For subjects randomized to the control group, the extraction socket will be bone grafted but allowed to heal for at least 4 months. Straumann allograft will be used for all socket grafting. The subject should return for Visit 2b implant surgery, at 17 weeks (± 1 week).

- Review inclusion/exclusion criteria
- Oral hygiene evaluation
- Concomitant medication
- Adverse event check
- Surgery/ bone grafting of extraction socket/implant placement
- Implant stability by RFA
- Verbal confirmation of pregnancy status, if applicable
- Standardized periapical radiographs
- Intra-oral photographs

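### Controls have no scheduled adverse-event check for 16 to 18 weeks after extraction, against 7 to 13 days in the test arm, so early adverse-event rates may not be comparable

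*Protocol*

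**What the plan says.** Protocol 6.1 places implant surgery (Visit 2b) "Immediately at tooth extraction or 17 weeks ± 1 weeks after tooth extraction" and Visit 3 at "10 days ± 3 days after implant surgery".

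The two arms reach Visit 2b differently (Protocol 6.4). In the test arm: "For subjects randomized to the test group, the implant will be placed immediately after tooth extraction and bone grafting of the extraction socket". In the control arm, "the extraction socket will be bone grafted but allowed to heal for at least 4 months". Protocol 6.3 to 6.5 and the Schedule of Assessments put an adverse-event check at Visits 2a, 2b and 3 in both arms. They list no visit, call or diary between 2a and 2b.

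The check looks back: "At each visit the Investigator should determine if any adverse events occurred since the last study visit" (Protocol 5.1.11), by interview and by review of dental and medical records. Collection runs from consent (Protocol 7), and an event is to be entered within five working days of the site learning of it (7.3.1).

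Adverse events are a secondary endpoint (Protocol 3.5), are among the outcomes that SAP section 3 lists for comparison between arms, and are a safety endpoint counted over the whole study (SAP 4.4). SAP section 8 summarises them descriptively by type, seriousness, relationship, severity, outcome and expectedness, but not by period.

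**The concern.** Visit 3 is anchored to implant placement, not to the first operation. In the test arm these are the same day. In the control arm they are about four months apart, so the first operation has no early check of its own. Bruising, swelling or pain that resolved untreated may leave no record, and the subject is first asked about it some four months later.

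At stake is whether early adverse-event rates can be read side by side. The planned tables cumulate over the whole study, so they would not show that one arm's early events were collected differently, and the SAP's section on bias (10.2) does not mention it. There is also a small group with weaker coverage still. A subject who never receives an implant is withdrawn without further follow-up (Protocol 5.3.2) and reporting stops at withdrawal (7.3). A control who leaves before Visit 2b may therefore have no check after extraction, yet stays in the ITT set used for adverse events (Protocol 8.3.2; SAP 10.1.1).

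**Working it through.** **Plan's own figures.** The plan gives no figure for adverse-event capture. The related figure it does give is length of follow-up (Protocol 3.8), which reproduces:
- Test: 3 + 12 + 48 = 63 months.
- Control: 4 + 3 + 12 + 48 = 67 months, or 4.5 + 3 + 12 + 48 = 67.5 months.

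**Days from extraction to the next scheduled check** (windows from Protocol 6.1):
- Test, Visit 3: 10 − 3 = 7 to 10 + 3 = 13 days, nominal 10.
- Control, Visit 2b: 16 × 7 = 112 to 18 × 7 = 126 days, nominal 17 × 7 = 119.
- Ratio: 112/13 = 8.6 at the least, 119/10 = 11.9 nominal, 126/7 = 18 at the most.

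**Other checks around the gap.**
- Test subjects are seen again for uncovering at 10 ± 3 weeks: 7 × 7 = 49 to 13 × 7 = 91 days. Since 91 < 112, they have at least two scheduled checks before a control has the first.
- The control arm's own Visit 3 falls 112 + 7 = 119 to 126 + 13 = 139 days after extraction, nominal 119 + 10 = 129. It serves the second operation, not the first.

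**What unequal capture could do (assumption only).** Take 52/2 = 26 per arm, a true early-event risk of 30% in both arms, and complete capture in the test arm. Expected test subjects with a recorded event: 26 × 0.30 = 7.8. For controls, with capture fraction c, the count is 7.8 × c and the apparent difference is 0.30 × (1 − c):

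| Control capture c | Controls with a recorded event | Apparent difference |
|---|---|---|
| 100% | 7.8 | 0 points |
| 90% | 7.02 | 3 points |
| 75% | 5.85 | 7.5 points |
| 50% | 3.9 | 15 points |

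None of these risks or capture fractions comes from the documents. The table shows the mechanism and a range, not an estimate.

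**The case against.** The strongest reply is that the gap is in scheduled contact, not in collection. Reporting is continuous from consent, the entry deadline runs from awareness rather than from the next visit, and Visit 2b must cover the whole interval by interview and record review. Changes in medication and procedures are also documented at each visit (Protocol 5.1.9). Serious or treated events should therefore leave a trace. This stands, and it narrows the point to mild, untreated, short-lived events. It does not remove it: the awareness clock cannot start for an event nobody reports.

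A reader might infer more, and four such inferences are not supported:
- *That control events are in fact under-captured.* The documents show a risk. They give no recall or event rate.
- *That the arms are checked unequally after the same surgery.* The test operation includes the implant; the control's first operation does not. After implant surgery both arms have the same 10-day visit. Some subjects also enrolled under a version with no stated grafting requirement (SAP 10.3.2), so for some controls the first operation may have been extraction alone. The gap in days is the same.
- *That delayed placement is made to look safer overall.* Controls have two operations and 4 to 4.5 months more follow-up, which could raise their cumulative counts. The net direction is not established.
- *That a control complication would not be found.* It would be asked about at Visit 2b, so the documents show delay, not absence. A study-visit schedule also does not show that routine care is missing.

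It is also fair that the safety analysis involves no hypothesis test.

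**Conclusion.** The point holds as a limit on comparability. After extraction, controls wait 112 to 126 days for a scheduled adverse-event check, against 7 to 13 days in the test arm, and neither document acknowledges this. Early rates, above all of mild and transient events, may not be comparable.

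The day counts follow directly from the visit windows. That events may be missed rests on one assumption: that untreated minor events are reported less completely after about four months than after 10 days. The number missed, and the net effect on whole-study incidence, cannot be computed from the documents. The primary endpoint and the success criterion are untouched. The matter deserves correction because adverse events are an outcome the plan says it will compare, and the remedy is cheap.

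**What to change.** **Subjects already past Visit 2b.** SAP 2.1 reports 53 randomised and 46 past the 12-month visit, so a 10-day contact after extraction is too late for this cohort. Amend SAP section 8, or, if the primary analysis has been run, record the change in the study report as SAP 10.6 provides. Tabulate adverse events by period, using the event dates that Protocol section 7 already requires:
- (a) extraction to before Visit 2b: controls only, marked as collected without a 10-day check, with the number who left before Visit 2b;
- (b) implant placement to Visit 3: both arms, noting that the test arm's window also contains the extraction;
- (c) after Visit 3: both arms, where the visit schedules match.

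Base the between-arm comparison on (c), and state the limitation for (a) and (b). A single table starting at implant placement would not do instead: that window holds extraction morbidity in the test arm only. The cost is one extra table, and (c) leaves the early post-operative period described rather than compared.

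**Protocol schedule, for any further enrolment.** In 6.1 and the Schedule of Assessments, add for controls an adverse-event and concomitant-medication contact at 10 ± 3 days after Visit 2a, with the same questions as Visit 3. A telephone call is enough for the data. The cost is minor site time for about 26 controls.

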6.2 Visit 1 - Screening Visit

This visit should be completed within 45 days prior to the tooth extraction (Visit 2a). An initial evaluation will be conducted to determine whether the subject meets the study inclusion and exclusion criteria and for collection of baseline data. This evaluation will include an appropriate medical and dental history, a clinical examination, and a radiographic evaluation. The screening evaluations and data collection can take place at several office visits as long as the visits are within 45 days of the surgery.

If the screening evaluations are not conducted within 45 days of the surgery, then the subject may be asked to re-consent and re-screen, as long as enrollment is still open.

In particular the following procedures and assessments will be performed and recorded at the screening visit:

- Informed consent
- Inclusion/exclusion criteria
- Demographics
- Pregnancy test (administered prior to randomization and before taking study required radiographs or CBCT scans)

- Medical and dental history
- Full mouth CBCT or panoramic radiograph with a localized CBCT scan
- Periodontal measurements (PPD and mSBI at adjacent teeth)
- Oral hygiene evaluation
- Concomitant medications
- Adverse event check
- Radiographic stent fabrication
- Intra-oral photographs

6.3 Visit 2a – Tooth Extraction/ Randomization

The following will be performed at this visit:

- Review inclusion/exclusion criteria
- Oral hygiene evaluation
- Concomitant medication
- Adverse event check
- Surgery/ tooth extraction
- Bone grafting of the extraction socket
- Randomization
- Intra-oral photographs

6.4 Visit 2b – Implant Surgery

The timing of Visit 2b will depend on the treatment group assigned during randomization. For subjects randomized to the test group, the implant will be placed immediately after tooth extraction and bone grafting of the extraction socket. For subjects randomized to the control group, the extraction socket will be bone grafted but allowed to heal for at least 4 months. Straumann allograft will be used for all socket grafting. The subject should return for Visit 2b implant surgery, at 17 weeks (± 1 week).

- Review inclusion/exclusion criteria
- Oral hygiene evaluation
- Concomitant medication
- Adverse event check
- Surgery/ bone grafting of extraction socket/implant placement
- Implant stability by RFA
- Verbal confirmation of pregnancy status, if applicable
- Standardized periapical radiographs
- Intra-oral photographs

6.5 Visit 3 - Immediate Post-Operative

The subject will be recalled for a post-operative visit at 10 days (± 3 days) following implant placement for a general assessment of wound healing and to remove sutures, if applicable.

In particular, the subject will have the following procedures and/or evaluations performed and documented:

- Suture removal, if necessary
- Oral hygiene assessment
- Concomitant medication
- Adverse event check

- Implant survival
- Intra-oral photographs

6.6 Visit 4 – Uncovering Implant

At 10 weeks (± 3 weeks) following implant surgery, the implant will be uncovered, a healing abutment placed, and the soft tissue adapted around the healing abutment. Note that implant loading (Visit 5) may be done at Visit 4 at the discretion of the investigator.

- Uncover implant, place healing abutment
- Impression or indexing the implant for indirect provisional fabrication
- Oral hygiene assessment
- Concomitant medication
- Adverse event check
- Implant survival
- Intra-oral photographs

6.7 Visit 5 – Implant Loading (BASELINE)

At 10 weeks (± 3 weeks) after implant surgery (2 - 4 weeks after uncovering the implant), and contingent upon good primary stability, the study implant will be loaded with a temporary abutment and restoration in appropriate occlusion. Note that uncovering of the implant (Visit 4) and implant loading can be done at the same visit at the discretion of the investigator.

The subject will have the following procedures and/or evaluations performed and documented:

- Temporary prosthesis seated
- Oral hygiene evaluation

- Concomitant mediation
- Adverse event check
- Implant stability by RFA
- Verbal confirmation of pregnancy status, if applicable
- Standardized periapical radiographs
- CBCT localized
- Implant survival and success
- Intra-oral photographs

6.8 Visit 6 – Definitive Impression

At 5 weeks (± 1 week) post loading, an impression (digital or conventional) will be taken for the fabrication of the final restoration.

The subject will have the following procedures and/or evaluations performed and documented:

- Impression for definitive fabrication
- Oral hygiene evaluation
- Concomitant mediation
- Adverse event check
- Implant survival
- Intra-oral photographs

